#### 7. Study Participants and Demographics

#### 7.1. Disposition of Participants and Withdrawals

The number of participants randomized and treated will be summarized by treatment group. The number and percentage of participants in the Safety, mITT, Completers, and PK Populations will be summarized by treatment group. The number and percentage of participants who completed the study and who prematurely discontinued the study will be summarized by treatment group. The reasons for study discontinuation will also be summarized.

All disposition information will be listed.

#### 7.2. Protocol Violations and Deviations

Protocol deviations will be listed.

#### 7.3. Demographics and Other Baseline Characteristics

Demographic variables such as age, sex (including child-bearing potential for female), ethnicity, and race, and baseline characteristics such as height, weight, and body mass index (BMI), highest Level of Education, ApoE4 Status, ApoE Genotype, and Mini Mental State Exam (MMSE) Total Score will be summarized by treatment group for the Safety and mITT (if different from Safety) Populations.

Categorical variables, such as sex, ethnicity, race, and level of education will be summarized using frequencies and percentages. Continuous variables such as age, height, weight, and BMI will be summarized using mean, SD, median, minimum, and maximum.

Medical history will be coded using the latest version of MedDRA at the time of database lock. Medical history information will be listed only.

Demographic information will also be listed.

#### 7.4. Exposure and Compliance

For all of the below formulas, i = individual participant for the entire treatment period.

• Total days of exposure will be calculated as:

$$\sum_{i}$$
 Days on Study Drug

• Study drug compliance will be calculated as:

$$\frac{\sum_{i} Actual \ Capsules \ Taken}{\sum_{i} Planned \ Capsules} \times 100$$

Compliance will be calculated using drug accountability data over the entire treatment period for each participant, up to treatment completion or discontinuation. Planned capsules will be calculated as 2 × the number of days between the first and last dose of study drug (inclusive).

Study drug exposure and compliance information will also be listed.

#### 8. Efficacy Analysis

All efficacy analyses are exploratory in nature. The intent of this plan is to run the analysis of covariance (ANCOVA) model described in section 8.1 at the time of the interim analysis and the mixed-model repeated measures (MMRM) model described in section 8.1 at the time of the final analysis. However, if the MMRM model fails to converge, the ANCOVA analysis (with both observed and observed + LOCF values) will be run in place of the MMRM model for the final analysis. A Day 182 visit will be considered out-of-window if it does not occur between study day 171 and study day 193 (inclusive).

For the final analysis, all efficacy analyses will be run using the mITT population and a subset of the efficacy parameters (ADAS-Cog 11, ADCS-ADL, MMSE, ADCS-CGIC) will be summarized using the Completers Population as a sensitivity analysis.

All figures will be based on the mITT population only. The following figures will be produced for each efficacy parameter (ADAS-Cog 11, ADCS-ADL, MMSE, ADCS-CGIC and the composite z-scores: Cognitive Composite score; Memory Composite score; Attention Composite score; and Executive Function Composite score):

- Line plot of change from baseline values.
- Line plot of least square mean change from baseline values.
- By-participant spaghetti plots of the change from baseline values.

#### 8.1. Composite z-scores

The composite z-scores (Cognitive Composite score; Memory Composite score; Attention Composite score; and Executive Function Composite score) defined in Section 6.1.8 will have their observed values and change from baseline summarized by visit.

Mean change from baseline within each of the four composite z-scores will be analyzed using a MMRM analysis with treatment as the main effect, visit, baseline z-score of the corresponding composite score, APOE  $\varepsilon 4$  (+ or -) status at baseline, and treatment by visit as an interaction term. All post-baseline analysis visits will be included in the model (Day 42, Day 98, and Day

182). An unstructured covariance matrix will be used to model the within-participant errors. The Kenward-Roger approximation will be used to estimate degrees of freedom.

The least squares (LS) mean change from baseline will be presented along with the associated 95% Confidence Interval (CI) within each treatment group. In comparing treatments (CT1812 100 mg/day minus placebo, CT1812 300 mg/day minus placebo, and the CT1812 groups combined versus placebo), LS mean differences in change from baseline will be presented along with associated 95% CIs and pairwise treatment *P*-values.

In the case of convergence issues, other covariance structures will be considered including (but not limited to) Toeplitz, compound symmetry (CS) and autoregressive (AR[1]) with each model fit to find the covariance structure with the best fit. The fit statistics will be compared for all covariance structures and the structure with the smallest Akaike information criterion will be retained as the preferred model.

For the interim analysis, ANCOVA model at each visit will be run in place of the MMRM. This model will include treatment as the main effect, baseline z-score of the corresponding composite scores, and APOE  $\varepsilon 4$  (+ or --) status at baseline. For endpoints where LOCF is used, the analyses will be repeated using only observed data.

The composite z-scores will also be listed.

#### 8.2. Mini Mental State Exam (MMSE)

The MMSE is a brief, screening instrument often used in clinical trials to assess dementia severity. The MMSE assesses several aspects of memory and cognitive functioning including orientation, attention, concentration, comprehension, recall, and praxis. The total possible score is 30, with high scores indicating less impairment.

Descriptive summaries of observed values and changes from baseline in the MMSE total score will be calculated by visit.

Change from baseline for MMSE will be analyzed using the same MMRM model described in Section 8.1, with the MMSE score in place of the composite score.

[figure not shown]
For the interim analysis, an ANCOVA model at each visit will be run using the same effects described in Section 8.1, with baseline MMSE score in place of the composite baseline score. For endpoints where LOCF is used, the analyses will be repeated using only observed data.

For the final analysis, MMSE will be summarized and analyzed for both the mITT Population and the Completers Population. Additionally, the change from baseline in MMSE will be summarized and analyzed for each subgroup defined in Section 6.1.10 using the mITT Population. For the subgroup analysis by ApoE status at Baseline, the APOE covariate will be excluded from the statistical model.

Results for MMSE will be listed.

#### 8.3. Alzheimer's Disease Assessment Scale-Cognition Subscale (ADAS-Cog 14)

The ADAS-Cog 14 is a widely used general cognitive measure in clinical trials of AD. The ADAS-Cog was developed as an outcome measure for dementia interventions; its primary

purpose was to be an index of global cognition in response to antidementia therapies. The ADAS-Cog assesses multiple cognitive domains including memory, language, praxis, and orientation. For this study, 13 items of the ADAS-Cog 14 will be assessed.

Descriptive summaries of observed values and changes from baseline in the ADAS-Cog 13 (ADAS-13) total score and ADAS-Cog 11 (ADAS-11) total score will be calculated by visit.

ADAS-13 and ADAS-11 change from baseline will be analyzed using the same MMRM model described in Section 8.1, with baseline ADAS-13 or ADAS-11 score in place of the composite baseline score.

For the interim analysis, an ANCOVA model at each visit will be run using the same effects described in Section 8.1, with baseline ADAS-13 or ADAS-11 score in place of the composite baseline score. For endpoints where LOCF is used, the analyses will be repeated using only observed data.

For the final analysis, ADAS-13 and ADAS-11 will be summarized and analyzed for both the mITT Population and the Completers Population. Additionally, the change from baseline in ADAS-13 and ADAS-11 will be summarized and analyzed for each subgroup defined in Section 6.1.10 using the mITT Population. For the subgroup analysis by ApoE status at Baseline, the APOE covariate will be excluded from the statistical model.

ADAS-Cog results will also be listed.

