#### 3.2. Sample Size and Power

The sample size justification in the protocol was as follows: for this trial, groups of 48 active-dosed participants per dose level are felt to give adequate sensitivity to detect AEs. A sample size of 48 active-dosed participants for each dose level (100 mg/day, 300 mg/day) has 91% power to detect at least one occurrence of any drug-related AE with a true prevalence in the treated population of 5%.

Additional participants may be added to replace participants with significant disruption to their visit schedule due to COVID or if there are unanticipated dropouts.

Additionally, for the primary exploratory efficacy analysis relating to the ADAS-COG 11 comparing the combined CT1812 treatment groups versus the placebo group, 48 participants per group provides 81% power to show a treatment difference of 3.0 points assuming a two-sided test at the alpha=0.05 level of significance, assuming a SD of 5.4 points, and a dropout rate of 15%.

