  - This blood draw will be performed at a local lab. The local lab will include onsite laboratory facilities for collection and processing. Participants consented to Protocol version 2.0 on or after their Baseline visit are not required to have the Biomarker samples drawn on Day 90 or Day 172.
- 19. The serum samples should not be collected on the same day as the lumber puncture.
- 20. Coagulation testing includes prothrombin time and INR.
- 21. Optional lumbar puncture: Participants may opt to undergo lumbar puncture as part of screening, after all other eligibility criteria have been reviewed and approved by the medical monitor, at least 24 hours before the Baseline visit and again at Day 182 (the end of the dosing period). LP on the Day 182 visit should be performed minimally 24 hours prior to the other the Day 182 visit procedures (e.g., Day 181) and prior to dosing on that day. The optional screening visit lumbar puncture must not be performed without Medical Monitor approval.
- 22. Urine should not be first morning void. See Laboratory Procedures Manual for sample handling.
- 23. Pregnancy testing should include an assessment of FSH levels.
- 24. C-SSRS Screening/Baseline version used at screening visit, Since Last Visit version used at all other visits.
- 25. The ADAS-Cog 13, NTB, ADCS-ADL, and MMSE will be conducted during screening period, and prior to dosing at other visits. The ADCS-CGIC will be conducted beginning at Day 1, and all other visits with the cognitive assessments.
- 26. All concomitant medications will be recorded from screening through Day 210.
- 27. During Screening (post-consent), only SAEs related to a study-specific procedure will be collected. For all related AEs of moderate or severe intensity ongoing at the end of the study, follow-up will continue until the event has resolved to baseline severity, the event is assessed as stable by the Investigator, or the participant is lost to follow-up or the participants withdraws consent.
- 28. Study drug accountability will be performed via capsule count.
- 29. Dosing on non-study visit days will be self-administered at home. On "Drug Dispensation" clinic visits drug accountability will be completed for the bottle returned by the participants and the "in office dose administration" will be taken for that visit from the newly assigned bottle. Study drug can be administered with, or without food.

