#### 6.1. Statistical Definitions and Algorithms

#### 6.1.1. Baseline

The last non-missing observation recorded on or before the first dose of study drug will be used

as the baseline observation for all calculations of change from baseline.

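### The efficacy models adjust for only one of two scheduled pre-dose scores; adding the screening score as a second covariate may sharpen them modestly at very small cost

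*SAP*

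**What the plan says.** The schedule tables in both documents place the cognitive battery, MMSE and ADCS-ADL at screening, Day 1, Day 42, Day 98 and Day 182. The note to SAP Table 1 reads: "The ADAS-Cog 13, NTB, ADCS-ADL, and MMSE will be conducted during screening period, and prior to dosing at other visits". The visit lists in Protocol 10.2.1 and 10.2.2 agree. ADAS-Cog 11 is a sum of 11 of the 13 items administered (SAP 6.1.8), so it too exists twice before dosing.

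SAP 6.1.1 defines baseline: "The last non-missing observation recorded on or before the first dose of study drug will be used". That is normally the Day 1 score; the screening score enters only if Day 1 is missing.

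SAP 8.1 fits an MMRM with treatment, visit, treatment by visit, one baseline score and APOE ε4 status. For the scale of main interest, SAP 8.3 says "ADAS-13 and ADAS-11 change from baseline will be analyzed using the same MMRM model", with the ADAS baseline substituted. SAP 8.2, 8.4 and 8.6 refer back to the same model. Neither document uses the screening score as a covariate, in an average or in a sensitivity analysis.

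SAP 6.1.3 makes the pooled ADAS-Cog 11 contrast at Day 182 the primary exploratory test. The 300 mg and 100 mg comparisons follow only if it is significant.

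**The concern.** A single administration of a cognitive scale carries day-to-day noise. A second score of the same scale, also taken before randomisation, can say more about the participant's underlying level and so explain more of the Day 182 outcome. Because it precedes randomisation, adjusting for it does not bias the treatment contrast. The SAP already accepts covariate adjustment, and these data are already collected.

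Precision matters most for the pooled ADAS-Cog 11 test, since missing significance there closes the route to both dose tests. The stated power of 81% leaves little reserve.

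**Working it through.** **Inputs from SAP 3.2.** The comparison is pooled, "comparing the combined CT1812 treatment groups versus the placebo group", under 1:1:1 allocation (SAP 3.5), so 2:1. The claim is that "48 participants per group provides 81% power to show a treatment difference of 3.0 points". The same sentence sets a two-sided 5% test, an SD of 5.4 and 15% lost to dropout.

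**Stated power reproduced.** Evaluable placebo: 48 × 0.85 = 40.8. Pooled active: 81.6. SE = 5.4 × √(1/40.8 + 1/81.6) = 1.035, and 3.0/1.035 = 2.90. Power is 82.6% by the normal formula and 82.0% by noncentral t (81.2% with 40 v 80). The stated 81% holds.

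**Effect of a second pre-dose score.** Let r1 be the correlation of Day 1 with Day 182, r2 of screening with Day 182, and ρ of screening with Day 1. Residual variance, as a fraction of the outcome variance:

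- one score: 1 − r1²
- both scores as covariates: 1 − (r1² + r2² − 2·r1·r2·ρ)/(1 − ρ²), which is 1 − 2r²/(1 + ρ) when r1 = r2 = r

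Example with r = 0.80 and ρ = 0.90: 0.360 falls to 1 − 1.28/1.90 = 0.326, a ratio of 0.906. The SD becomes 5.4 × √0.906 = 5.14.

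The documents report none of these correlations; all are assumptions. SAP 3.2 does not say which SD 5.4 is. The table takes it as the residual SD of the planned model, so planned power is 82.0% (noncentral t).

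| r1 | r2 | ρ | Change in residual variance | SD | Power |
|---|---|---|---|---|---|
| 0.70 | 0.70 | 0.90 | −5.1% | 5.26 | 83.9% |
| 0.70 | 0.70 | 0.85 | −7.8% | 5.19 | 84.9% |
| 0.80 | 0.80 | 0.90 | −9.4% | 5.14 | 85.5% |
| 0.80 | 0.80 | 0.85 | −14.4% | 5.00 | 87.4% |
| 0.80 | 0.80 | 0.80 | −19.8% | 4.84 | 89.4% |
| 0.80 | 0.78 | 0.90 | −5.3% | 5.26 | 84.0% |
| 0.80 | 0.75 | 0.90 | −1.3% | 5.36 | 82.5% |
| 0.80 | 0.72 | 0.90 | 0.0% | 5.40 | 82.0% |

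The first four rows are the middle cases. They correspond to 48 × 5.1% ≈ 2 up to 48 × 14.4% ≈ 7 participants per arm. They take screening to predict Day 182 as well as Day 1 does. The last three rows relax that: when r2 = r1·ρ (0.80 × 0.90 = 0.72), screening adds nothing. With r1 of 0.70-0.80 and ρ of 0.80-0.90, the gain vanishes once r2 falls below r1 by r1(1 − ρ), which is 0.07 to 0.16.

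**If 5.4 is instead the SD of raw change.** The outcome variance is 5.4²/[2(1 − r1)] = 72.9 at r1 = 0.80. The one-score SD is √(72.9 × 0.360) = 5.12, power 85.8%. With both scores (r2 = 0.80, ρ = 0.90) it is √(72.9 × 0.326) = 4.88, power 88.9%.

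**Averaging the two scores.** As a single covariate, the mean leaves 1 − (r1 + r2)²/[2(1 + ρ)]. At (0.80, 0.75, 0.90) this is 0.368 against 0.360, a 2.2% rise. At (0.80, 0.72, 0.90) it is 0.392, an 8.9% rise. Averaging can therefore lose precision where a separate covariate would not.

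**Cost.** The additional degree of freedom changes power by less than 0.01 percentage points.

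This is a two-group approximation at Day 182 among the evaluable. It ignores what the MMRM draws from Days 42 and 98.

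**The case against.** The strongest reply is that nothing here is wrong. A baseline-adjusted MMRM with unstructured covariance and Kenward-Roger degrees of freedom is valid, one baseline covariate is conventional, and the baseline rule is clear. The primary objective is safety, the secondary is CSF biomarkers, and SAP 8 labels all efficacy analyses exploratory. The test already meets its 81% target. All of this stands, and it limits how much weight the point deserves.

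The second reply also stands: the gain may be nil. Protocol 10.2.1 allows screening up to 60 days before Day 1, and it may be the participant's first exposure to the battery, so screening may predict Day 182 less well. A reader might infer that the second score is certain to narrow the interval. The documents do not support that: narrowing is expected only if screening predicts Day 182 beyond Day 1, and it is not assured in any one sample.

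Third, screening MMSE is subject to the 18-26 entry criterion, so its two readings are not interchangeable. This argues against averaging; it does not bias a separate covariate. Practice effects between the readings apply to all arms alike.

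Fourth, several SAP sections need editing, and the interim ANCOVA keeps one baseline covariate. The interim and final models already differ by design, so this is an administrative cost only.

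**Conclusion.** The point holds as an optional gain in efficiency. Two pre-dose scores are scheduled and the models normally use one. For assumed ρ of 0.80-0.90, r1 of 0.70-0.80, and r2 anywhere from r1 down to r1·ρ, residual variance at Day 182 falls by 0 to about 20%, and power for 3.0 points goes from about 82% to 82-89%. Middle cases give about 5-14% and 84-87%. These figures treat 5.4 as the planned model's residual SD and were worked only for ADAS-Cog 11; gains on the other scales were not computed.

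A reader might infer that the planned test is biased, invalid or underpowered against its own target. The documents support none of these: the contrast is randomised and properly adjusted, and the stated power reproduces.

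**What to change.** Before final unblinding, amend SAP 6.1.2, 8.1-8.4 and 8.6 as follows:

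- Add the screening score of the same scale as a second fixed covariate beside the Day 1 baseline. For composites, z-score the screening components with the same baseline mean and SD.
- Keep Day 1 as the reference for change from baseline, and do not average the two readings.
- If one of the two readings is missing, set it to the other, so that nobody leaves the model. This fits SAP 6.1.1, which already falls back on screening when Day 1 is missing.

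ADCS-CGIC (SAP 8.5) has no baseline score and is unaffected. The cost is one degree of freedom per model and a small SAP edit, with no new data.

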#### 3.5. Method of Assigning Participants to Treatment Groups

Participants will be randomized in a 1:1:1 ratio to CT1812 100 mg/day, CT1812 300 mg/day or placebo. The placebo will be identical in appearance to the active CT1812. The unblinded statistician assigned to the trial will generate a randomization list with the appropriate number of 4--digit individual study identification numbers (IDs) for each arm, randomly assigned to one of the treatment arms.

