#### 4.1. Introduction

Data processing, tabulation of descriptive statistics, calculation of inferential statistics, and graphical representations will be performed primarily using SAS (release 9.4 or higher). If the use of other software is warranted, the final statistical methodology report will detail what software was used for what purposes.

Continuous (quantitative) variable summaries will include the number of participants (n) with non-missing values, mean, standard deviation (SD), median, minimum, and maximum. Other statistics such as coefficient of variation (%CV), quartiles, confidence intervals (CIs), and number of missing values may be added as appropriate.

Categorical (qualitative) variable summaries will include the frequency and percentage of participants who are in the particular category or each possible value. In general, the denominator for the percentage calculation will be based upon the total number of participants in the study population within each treatment group, unless otherwise specified. The denominator for by-visit displays will be the number of participants in the relevant study population with non-missing data at each visit.

The minimum and maximum will be reported with the same degree of precision (i.e., the same number of decimal places) as the observed data. Measures of location (mean and median) will be reported to 1 degree of precision more than the observed data. Measures of spread (SD) will be reported to 2 degrees of precision more than the observed data.

Percentages will be presented to 1 decimal place, unless otherwise specified.

Unless otherwise indicated, all statistical tests will be conducted at the 0.05 significance level using 2-tailed tests, and P-values will be reported. A P-value of  $\leq$ 0.10 but >0.05 will be considered evidence of a trend. Corresponding 95% CIs will be presented for statistical tests.

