#### 6.1.3. Multiple Comparisons

Although all of the clinical efficacy analyses for this study are exploratory in nature, the ADAS-Cog 11 least square mean change from baseline analysis is considered the primary exploratory analysis of interest compared to the other clinical efficacy analyses. The primary exploratory analysis of the ADAS-Cog 11 will compare the least square mean change from baseline value for the two active arms combined to the least square mean change from baseline value for the placebo arm at day 182, using a two-sided test at the alpha=0.05 level of significance. If the primary exploratory analysis of the ADAS-Cog 11 is statistically significant, then the following comparisons will be made using the least square mean change from baseline values and the same model as for the primary analysis:

- 1) 300 mg CT1812 versus placebo;
- 2) 100 mg CT1812 versus placebo.

Each comparison will be conducted using a two-sided test at the alpha=0.05 level of significance. This fixed sequence testing procedure will control the overall level of significance for this outcome.

All other clinical efficacy analyses will be conducted using two-sided tests at the alpha=0.05 level of significance. No adjustments will be made for multiple comparisons and all other p-values will be considered nominal.

[figure not shown]

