#### 8.8. Biomarker Changes

Targeted measurements of several protein biomarkers in CSF and plasma will be made, including the following:

Biology	Biomarker	Biofluid
	Αβ42, Αβ40, Αβ42/40 ratio	CSF, plasma
	Total Tau	CSF
AD progression disease	pTau181	CSF, plasma
	pTau217	plasma
	Brain derived Tau (BD-Tau)	plasma
	Neurogranin	CSF
Synaptic function	Synaptotagmin 1, SNAP25	CSF
Neuroinflammation	GFAP	CSF, plasma
Neurodegeneration	NFL	CSF, plasma
Other	Alpha-Syn	CSF

For A $\beta$ 40 and A $\beta$ 42, it is expected to see decreases in the change from baseline values with CT1812 treatment at 6 months. For all remaining biomarkers, it is hypothesized that changes will be observed over the 6-month treatment period.

Descriptive summaries of observed values and changes from baseline for each plasma and CSF

biomarker will be calculated by visit.

Plasma samples will be analyzed at baseline (V2), V11 (Day 98), and Day 182. Assuming data for more than one post-baseline sample is available, the change from baseline for each plasma biomarker will be analyzed using the same MMRM model described in Section 8.1. If only one post-baseline sample is available, then the ANCOVA model detailed below will be used.

For the interim analysis, for analysis of the CSF biomarkers at the final analysis, and in the scenario where only one post-baseline plasma biomarker sample is available at the final analysis, an ANCOVA model of change from baseline values will be run using the same effects described in Section 8.1. For CSF, only screening (V1) and V14 (Day 182) biomarker samples were collected and biomarkers will be measured in CSF from V1 and V14 and will be analyzed in the final analysis.

For the analysis of phospho-tau proteins performed for the interim analysis only, ANOVA analysis of the log2 (fold change from baseline) will be used to assess significance of drug effects.

For the final analysis, the change from baseline in each biomarker will be summarized and analyzed for the "Measurable PK at Multiple Timepoints" subgroup. Additionally, for just the A $\beta$ 40 and A $\beta$ 42 biomarkers, the change from baseline will be summarized and analyzed by the "MMSE at Baseline" subgroup. The following rules will apply to the subgroup analyses:

- If less than 10 participants fall into any one treatment group/level of a subgroup, then the corresponding summary/analysis for that subgroup will not be conducted.

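### The efficacy subgroup analyses give within-level p-values but no treatment-by-subgroup contrast, so they cannot show whether the CT1812 effect differs between levels

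*SAP*

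**What the plan says.** SAP 6.1.10 defines eight two-level factors (sex, baseline MMSE, age, ApoE status, baseline pTau217, pre/post COVID, region, AChE inhibitor or memantine use) and one further set of participants with measurable PK. For that last set it says that a comparison with those outside it is not of interest.

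Five efficacy endpoints go through every subgroup. SAP 8.3 says that "change from baseline in ADAS-13 and ADAS-11 will be summarized and analyzed for each subgroup", and 8.2 that "the change from baseline in MMSE will be summarized and analyzed for each subgroup defined in Section 6.1.10 using the mITT Population". Sections 8.5 and 8.6 do the same for ADCS-CGIC and ADCS-ADL.

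All use the MMRM of SAP 8.1, whose only interaction is treatment by visit. It reports LS mean differences with 95% CIs and p-values for three comparisons: each dose versus placebo, and the doses combined versus placebo. For the ApoE subgroup, the APOE covariate is dropped. That implies a separate model within each level, although the SAP does not say so outright.

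SAP 8.8 has a size rule: "If less than 10 participants fall into any one treatment group/level of a subgroup", the corresponding analysis is not done. It is written for biomarker subgroups; 8.2, 8.3, 8.5 and 8.6 have no equivalent.

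SAP 4.1 says that a p-value above 0.05 and up to 0.10 "will be considered evidence of a trend". The sentence is general and makes no exception for subgroups.

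On error control, SAP 6.1.3 says: "All other clinical efficacy analyses will be conducted using two-sided tests at the alpha=0.05 level of significance". It adds that p-values outside the ADAS-Cog 11 sequence are unadjusted and nominal. SAP 8 calls all efficacy analyses exploratory.

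**The concern.** A subgroup analysis asks whether the treatment effect differs between levels. The plan instead asks, in each level separately, whether the effect differs from zero. The two answers can diverge widely: when the effect is the same in everyone, one half of the trial will often reach 0.05 and the other will not, purely because each half is small. A reader of the tables would then see an apparent responder group that the data do not support.

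Two features add to this. Small levels can be modelled without any minimum size, although the SAP guards against that for biomarkers. And the trend label doubles, from 5% to 10% per test, the rate at which a null result attracts a positive description.

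**Working it through.** **Inputs.** SAP 3.2: "48 participants per group provides 81% power to show a treatment difference of 3.0 points", with SD 5.4, two-sided 0.05 and 15% dropout, for the combined doses versus placebo. SAP 3.5 gives 1:1:1 allocation, so the pooled contrast is 2:1. The documents give neither level shares nor correlations between endpoints; those below are assumptions. Two-sample t-tests stand in for the MMRM.

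**The plan's own figure.** Evaluable numbers are 0.85 × 96 = 81.6 and 0.85 × 48 = 40.8. With 80 versus 40, SE = 5.4 × √(1/80 + 1/40) = 1.046 and 3.0/1.046 = 2.87; noncentral-t power is 81.2%. With 81.6 versus 40.8 it is 82.0%. The stated 81% is reproduced.

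**Number of tests.** Eight factors × 2 levels + 1 PK set = 17 sets. 17 × 5 endpoints × 3 comparisons = 255 p-values at Day 182, or 765 over Days 42, 98 and 182. Under no effect, the expected count among the 255 is 255 × 0.05 = 12.75 at 0.05 and 25.5 at 0.10.

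**Chance of at least one positive result under no effect (null simulation, Day 182).**

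| Family | p ≤ 0.05 | p ≤ 0.10 |
|---|---|---|
| ADAS-Cog 11, pooled vs placebo, eight independent even splits | about 37% | about 60% |
| Same contrast, all 17 sets, even or uneven shares | 36–39% | 58–63% |
| ADAS-Cog 11, three comparisons | 60–63% | 82–84% |
| ADAS-11 and ADAS-13, three comparisons | 69–72% | 89–91% |
| All 255 tests, either direction | 94–98% | above 99% |
| All 255 tests, favouring CT1812 only | 63–76% | 79–90% |

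From the second row on, level shares are all 50% or a mix of 10% to 60%. Assumed endpoint correlations are 0.3 to 0.7, except 0.95 between ADAS-11 and ADAS-13.

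**False heterogeneity under a uniform effect.** Take the plan's 3-point effect in everyone and an even split, 41 versus 20.5 per level.
- SE within a level = 5.4 × √(1/41 + 1/20.5) = 1.461; power is 52%.
- The levels contain different participants, so the chance that exactly one is significant is 2 × 0.52 × 0.48 = 0.50 per factor.
- The factors share participants, so the chance over eight was simulated: at least one factor is discordant in about 89% of trials. In the same setting an interaction test at 0.05 flags at least one factor in about 32%.

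**Smaller levels.** A 20% level holds about 0.20 × 41 = 8 placebo participants and has about 25% power for 3 points. A 10% level holds about 4 and has about 15%. The 8.8 rule would exclude both.

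**What the alternatives deliver.**
- Interaction SE at an even split = 1.461 × √2 = 2.066. For a 3-point interaction, 3/2.066 = 1.45, and power is Φ(1.45 − 1.96), about 31%.
- Chance of at least one interaction p ≤ 0.05 under no effect: 1 − 0.95^8 = 34% over eight factors if independent (33–38% simulated), and 1 − 0.95^6 = 26% over six.
- Applying the 10-per-cell rule to within-level ADAS-Cog 11 tests, with the mixed shares, lowers 39% to 32%.

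**The case against.** The best defence is that the SAP already qualifies these results. Efficacy is exploratory, p-values outside the ADAS-Cog 11 sequence are nominal, and the primary objective is safety. That stands: no confirmatory error rate is breached, and what remains is a risk of over-reading.

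The plan also does not offer p-values alone. The 8.1 model reports differences with 95% CIs, so much of the per-level estimation is already there. That stands too; what is missing is the comparison between levels.

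Interaction tests bring false positives of their own, about one in three over eight factors, so they do not control the family. This is correct. Their advantage is that they address the right question and are not driven by the size of each level.

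Some factors do not suit an interaction test. AChE inhibitor or memantine use is defined over the treatment period, and pre-COVID status depends on the date of completion or withdrawal; both turn on events after randomisation. The fix leaves them out.

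Two stronger readings are tempting. A reader might infer that spurious subgroup findings are near certain. That holds only for the full set of 255 Day 182 tests in either direction (or the larger all-visit set), not for ADAS-Cog 11 with the pooled contrast. A reader might also infer that the subgroups will pick the population for the next trial; neither document says so.

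**Conclusion.** The point holds as a worthwhile, inexpensive improvement to exploratory analyses, not as a breach of error control. The five-endpoint subgroup plan contains no contrast that can show effect modification. It leaves the size rule in the biomarker section and lets the trend label reach subgroup results.

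The false-heterogeneity result matters most: with the sponsor's own effect size and SD, a uniform benefit would look level-specific for at least one factor in about nine trials out of ten. That figure and the 37% and 60% rest on eight independent, even splits. Real shares may be uneven, and factors such as ApoE, pTau217 and baseline MMSE may be related. That the models are fitted level by level is inferred from the handling of the APOE covariate.

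**What to change.** - For the six baseline-defined factors (sex, baseline MMSE, age, ApoE, baseline pTau217, region), fit one MMRM per factor in all mITT participants with treatment × visit × subgroup and all lower-order terms. Name ADAS-Cog 11 at Day 182 as the main subgroup analysis.
- Report the pooled-minus-placebo difference in each level with its 95% CI, and the difference between levels with its CI and a nominal interaction p-value. Omit within-level p-values.
- Keep AChE inhibitor or memantine use, pre/post COVID and the measurable-PK set descriptive. The first two depend on post-randomisation events, and the PK set has no comparison level by design.
- Extend the 8.8 minimum of 10 per treatment group and level to 8.2, 8.3, 8.5 and 8.6.
- State in 4.1 that the trend label does not apply to subgroup results.

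The cost is SAP wording and a modest change to the subgroup program. The downside is low interaction power (about 31% for a 3-point interaction at an even split) and a remaining chance of a false positive, about 26% over six factors if independent. The SAP should state both and call the results hypothesis-generating.
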